This protocol describes the IP7-PACIFIC trial and provides information about procedures for enrolling participants to the trial. The protocol should not be used as a guide for the treatment of other participants; every care was taken in its drafting, but corrections or amendments may be necessary. These will be circulated to investigators in the study, but centres enrolling participants for the first time are advised to contact the Trial Coordination centre to confirm they have the most recent version. Problems relating to this trial should be referred, in the first instance, to the Trial Coordination centre.

This trial will adhere to the principles outlined in the UK Policy Frame Work for Health and Social Care Research and the International Conference on Harmonisation Good Clinical Practice (ICH GCP) guidelines. It will be conducted in compliance with the protocol, the Data Protection Act 2018 and other regulatory requirements as appropriate.

ABBREVIATIONS

AE	Adverse Event	
bp	Biparametric	
CI	Chief Investigator	
CRF	Case Report Form	
DMC	Data Monitoring and Ethical Committee	
DRE	Digital Rectal Examination	
eCRF	Electronic Case Report Form	
EDC	Electronic data capture	
EPIC	Expanded Prostate Index Composite	
HADS	Hospital Anxiety and Depression Scale	
HRA	Health Research Authority	
ICHNT	Imperial College Healthcare NHS Trust	
ICMJE	International Committee of Medical Journal Editors	
ICTU	Imperial Clinical Trials Unit	
ISUP	International Society of Urologic Pathology	
ITT	Intention to Treat	
LSLV	Last Subject Last Visit	
MDT	Multidisciplinary team	
mp	Multi-parametric	
MRI	Magnetic Resonance Imaging	
NHS	National Health Service	
NHSCR	National Health Service Care Register	
PSA	Prostate Specific Antigen	
PSS	Personal Social Services	
QA	Quality Assurance	
QALAY	Quality-Adjusted Life-Year	
QC	Quality Control	
REC	Research Ethics Committee	
RGIT	Research Governance and Integrity Team	
SAE	Serious Adverse Event	
SAP	Statistical Analysis Plan	
SOP	Standard Operating Procedure	

TMG	Trial Management Group
TSC	Trial Steering Committee

Table of Contents

RES	EAF	RCH REFERENCE NUMBERS	2
CON	TA	CT LIST	3
ABB	RE	VIATIONS	6
TRIA	L S	UMMARY	10
1.		BACKGROUND	13
2.		OBJECTIVES AND ENDPOINTS	15
	2.1	Primary Objectives	15
	2.2	Secondary Objectives	16
	2.3	Primary Endpoint	17
	2.4	Secondary Endpoints	17
	2.5	Summary Table of Objectives and Endpoints	19
3.		STUDY DESIGN	19
•••	3.1	Design	20
4.	-	PARTICIPANT ENTRY	21
	41	Study setting and population	21

(Randomisation 1)	be recommended as an alternative to multiparametric	
	MRI (mpMRI) for the detection of clinically significant	
	prostate cancers in patients at risk	
Primary Objective	To determine whether image-fusion targeted biopsy is	
(Randomisation 2)	better than visual-registration (cognitive) targeted	
	biopsy at detecting clinically significant prostate	
	suspicious MRI	
Secondary Objectives	To evaluate the NHS healthcare burdens of boMRI	
	compared to mpMRI, and image-fusion technology	
	compared to visual-registration targeting, in terms of	
	adverse events, proportion of patients biopsied and	
	proportion of patients diagnosed with clinically	
	significant and insignificant cancers that do not require	
	liealment	
	To determine the impact of bpMRI and image-fusion	
	targeting on detecting clinically significant cancer using	
	other commonly used histological definitions of clinical	
	significance	
	To evaluate NHS costs and cost-effectiveness of	
	bpinkl compared to mpinkl, and image-fusion	
	well as model the various combinations of MRI and	
	targeting strategies	
DESIGN	Randomised controlled trial	
	2000	
	3600	
INCLUSION AND		
EXCLUSION CRITERIA		
Randomisation 1	Inclusion	
	- Age 18 years or above (no upper limit)	
	- Patients with a prostate (either cis-male gender or	
	hormone use at all)	
	- Referred to hospital and advised to undergo a prostate	
	MRI because of an abnormal digital rectal examination	
	(regardless of PSA level) and/or an elevated PSA	
	(within 6 months of screening visit)	
	PSA >/=3.0ng/ml for age 50-69 years	

	PSA >/=5.0ng/ml for age >/=70 years If family or ethnic risk for prostate cancer, PSA >/=2.5ng/ml for age 45-49 years
	 Exclusion PSA >50ng/ml Prior prostate MRI or prostate biopsy in the two years prior to screening visit Prior diagnosis of prostate cancer Contraindication to MRI or gadolinium contrast Previous hip replacement to both hips Contraindication to performing a biopsy guided by a transrectal ultrasound probe
Randomisation 2	Inclusion Visible suspicious finding on mpMRI or bpMRI from randomisation 1 requiring a targeted biopsy (MRI score 3, 4, 5 on either Likert or PIRADS [latest version as defined in MRI Reporting SOP] schema) Exclusion As above for randomisation 1 Patient refusal for biopsy
MAIN STUDY PROCEDURES	 Randomisation 1 Multi-parametric MRI compared to biparametric MRI Randomisation 2 Targeted biopsy performed using image-fusion targeted and systematic biopsies compared to visual-registration targeted and systematic biopsies in patients with visible suspicious finding on either bpMRI or mpMRI. Duration of follow-up: For up to 12 weeks after enrolment.
OUTCOME MEASURES (PRIMARY ENDPOINTS)	
Randomisation 1	Proportion of clinically significant cancers, defined as any amount of Gleason >/=3+4 (ISUP Grade Group >/=2) on biopsy, detected in the randomised population of patients at risk.
Randomisation 2	Proportion of clinically significant cancers, defined as any amount of Gleason >/=3+4 (ISUP Grade Group >/=2) on biopsy, detected in the randomised population of patients biopsied for a suspicious MRI.
OUTCOME MEASURES (SECONDARY ENDPOINTS)	
	Proportion recommended for biopsy in randomised arm Proportion actually biopsied in each randomised arm

Proportion diagnosed with clinically insignificant prostate cancer (defined as any Gleason 3+3=6 [ISUP Grade Group 1])
Proportion of clinically significant and insignificant cancers using other histological definitions of clinical significance - PROMIS 1 and 2 - any Gleason >/=4+3 [ISUP Grade Group >/=3] - Gleason >/=3+4 [ISUP grade Group >/=2] or any Gleason 3+3 [ISUP Grade Group 1] of >/=6mm - Gleason >/=3+4 [ISUP grade Group >/=2] with >/=10% pattern 4 OR presence of cribriform pattern OR presence of intraductal components
Detection rates for each randomised group of known prognostic risk categories. These are D'Amico, National Comprehensive Cancer Network (NCCN) and Cambridge Prognostic Groups (CPG).
Adverse events and patient reported outcomes
Outcomes by centre stratified by size and type of MRI scanner, route of biopsy and amount of systematic sampling.
Healthcare resource utilisation, costs and cost- effectiveness of using fastMRI compared to mpMRI and image-fusion compared to cognitive targeted biopsies
Consent for linkage to national databases to collect medium and long-term outcomes including new diagnostic tests, prostate cancer diagnoses and treatments, deaths and prostate cancer deaths

Since biopsies can cause side-effects such as pain, bleeding and infection, a non-suspicious mpMRI can allow some men to avoid an invasive biopsy as the probability of clinically significant prostate cancer is low. In the UK, a decision on whether to carry out a biopsy is then based on the mpMRI findings in combination with other clinical factors: about a guarter can avoid an immediate biopsy due to a low risk of harbouring clinically significant prostate cancer. In most centres, if a biopsy is indicated, it is guided by ultrasound with the operator estimating where to deploy the biopsy needle in order to take tissue samples; what is commonly referred to as visual-registration targeting. We want to test two major changes that might further improve this new pathway.

First, mpMRI takes 40 minutes, requires intravenous gadolinium contrast and costs £239 (NHS HRG 2020 Tariff) in the UK NHS. Administration of gadolinium requires medical supervision due to a risk of anaphylaxis. Further, there is concern about its deposition in the brain although there is uncertainty about whether this causes harm. In addition, many hospitals struggle with scanner time and this can lead to patients with suspected prostate

cancer and other medical conditions waiting longer [Royal of College of Radiology 2017]. A 15 minute, bpMRI that does not involve injection of gadolinium contrast and costs £141 (NHS HRG 2020 Tariff) might be as accurate as mpMRI in ruling-out and detecting clinically significant prostate cancer.

Further, capacity constraints mean that many hospitals are unable to scan all the men referred with suspected prostate cancer quickly enough to meet NHS cancer waiting time targets. Indeed, the extra prostate mpMRI scans might lead to patients with other medical conditions having to wait longer. An April 2017 Royal College of Radiology report stated that of 53 organisations surveyed, the mean anticipated increase in workload for scanning was 13%. This survey was conducted prior to the PROMIS study was published and might be an underestimate as it did not take into account the number of expected prostate mpMRI scans. A bpMRI would free up over 4,500 days of scanner time every year within the NHS, equivalent to approximately 100,000 extra bpMRI scans per year. This is because examination time for scanning is different to MRI time slots which have to include the time taken to safety-check, set-up intravenous access and set up the contrast pump, get patients into the magnet/positioned, perform planning sequences, localisers, and after scanning getting the patient off the table. The immediate cost saving to NHS commissioners in tariff payments of not having to use contrast-enhanced mpMRI would be £6.7 Million every year, with further potential savings from not requiring on-site medical cover and reductions in the length of time to review scans as there are fewer images to look at, so helping to free up expert radiology time. The NHS will also be able to scan more patients in a timely fashion.

Second, for those men needing a targeted biopsy, visual-registration requires highly skilled operators that are not available everywhere. This means that clinically significant cancers might be missed. Image-fusion technology that overlays MRI and ultrasound images might improve the detection of clinically significant prostate cancer as they can guide the biopsy needle to within 2-3mm accuracy.

Figure 2. MRI to ultrasound image fusion for targeted biopsy. The lesion is not visible on ultrasound so visual-registration targeting would be based on the operator looking at the MR-images on a separate screen (which is often in a different room) and then estimating where to deploy the needles. With image-fusion, tissue deformation and rotation can be taken into account with the lesion demonstrated as an overlaid contour on the ultrasound.

bpMRI and mpMRI

Systematic reviews of non-randomised comparisons have shown bpMRI might be as accurate as mpMRI [Woo et al, 2018; Niu et al, 2018; Kang et al, 2018; Chen et al, 2017; Alabousi et al, 2019]. The most recent included studies up to October/2017 [Alabousi et al, 2019] (25 mpMRI studies with 7000 patient vs. 12 bpMRI studies with 2716 patients) showed no significant difference in pooled sensitivity (mpMRI: 86%, 95%CI 81–90; bpMRI: 90%, *CONFIDENTIAL*

IP7-PACIFIC Protocol No: 22CX7488	Imperial College London	V3.0 18 th December 2023
-----------------------------------	-------------------------	-------------------------------------

95%CI 83–94) or specificity (mpMRI: 73%, 95%CI 64–81; bpMRI: 70%, 95%CI 42–83). Our updated (Oct/2017-July/2019) systematic review reinforced this finding from 11 further studies with 3488 patients [Bass et al, 2021]. This is reinforced by further analyses of our paired-cohort studies, PROMIS and PICTURE. PROMIS used template mapping biopsies as a reference test and blinding between those assessing imaging and biopsy in 576 men. It has shown similar sensitivity between mpMRI and bpMRI (95% vs. 94%) and specificity (38% vs. 37%) [Kirkham et al, 2019]; these data are supported by the PICTURE [Eldred-Evans et al, 2019]. Recently, another case series of 264 UK patients showed that bpMRI detected 93.5% of clinically significant prostate cancers compared to 94.6% with mpMRI [Zawaideh et al, 2020]. The BIDOC study has also shown high accuracy of bpMRI [Boesen et al, 2018].

Whilst useful and encouraging the studies are limited in informing NHS practice. For example, in many studies the radiologist gave a bpMRI score first. They then gave a score based on the mpMRI of the same men. In a number of studies, there may have been reporter bias, as the radiologists knew that the actual decision for doing a biopsy would be based on the mpMRI result. As a result, we do not know whether radiologists would score the bpMRI, and whether urologists would make similar recommendations about biopsy, if the mpMRI was not available. Clinicians and guideline committees are aware of this and in order to provide convincing high quality, reliable evidence concerning a recommendation about use of bpMRI that would change routine practice, a randomised controlled trial is required in which prostate cancer detection is compared in men receiving only bpMRI to men receiving mpMRI. Indeed, the systematic reviews all caution against applying these results to clinical practice due to heterogeneity among the included studies and lack of level 1 clinical utility comparative studies to assess biopsy avoidance, clinically significant prostate cancer detection and over-diagnosis of clinically insignificant prostate cancer [Brizmohun et al, 2018; [name] et al, 2018; Coakley et al, 2017; Schoots et al, 2020].

Visual-registration and image-fusion targeted biopsies

We [Valerio et al, 2015; Bass et al, 2020] and others [Verma et al, 2017; Gayet et al, 2016; Sarkar et al, 2018; Tang et al, 2018; Wegelin et al, 2017] have conducted systematic reviews showing that further research is required on image-fusion. We recently updated the systematic review by Wegelin et al with inclusion dates updated to Dec/2015 to July/2019); we found 32 further studies with image-fusion and 6 studies with visual-registration showing residual uncertainty remains and higher quality comparative studies are required [Bass et al, 2021]. The Chief Investigator has also led the Wellcome-funded SmartTarget [Hamid et al, 2019] and NIH PICTURE [Simmons et al, 2018] paired-cohort validation studies showing image-fusion targeting increased clinically significant prostate cancer detection by approximately 10-15% compared to visual-registration alone. Again, high quality randomised comparative data assessing clinical utility are now required to definitively determine clinical and cost-effectiveness of image-fusion targeting over visual-registration if guidelines and clinical practice are to change.

2. OBJECTIVES AND ENDPOINTS

2.1 Primary Objectives

Randomisation-1: bpMRI versus mpMRI

IP7-PACIFIC Protocol No: 22CX7488	Imperial College London	V3.0 18 th December 2023
-----------------------------------	-------------------------	-------------------------------------

In those patients suspected to have prostate cancer, to determine whether bi-parametric MRI (bpMRI), compared to multi-parametric MRI (mpMRI), is able to accurately rule-out and detect clinically significant prostate cancer (any Gleason score >/=7 [ISUP Grade Group >/=2]), without increasing the number of patients biopsied or diagnosed with clinically insignificant prostate cancer.

Randomisation-2: Visual-registration targeting versus image-fusion targeting

In those patients recommended to have a prostate biopsy due to a suspicious MRI (bpMRI or mpMRI), to determine if new technology using MRI to ultrasound image-fusion to carry out targeted prostate biopsies is better at detecting clinically significant prostate cancer (any Gleason score >/=7 (any Gleason score >/=7 [ISUP Grade Group >/=2]), compared to biopsies carried out using visual-registration targeting.

2.2 Secondary Objectives

Clinical

- To determine whether bpMRI is non-inferior to mpMRI in terms of the proportion of patients recommended for biopsy.
- To evaluate adverse events from MRI scans and biopsies.
- To determine the differences between proportions of patients diagnosed with clinically insignificant prostate cancers following bpMRI or mpMRI.
- To measure the proportion of patients declining a biopsy when advised to have it and the proportion of patients who choose to have a biopsy when it is not advised by their clinical team.
- To determine the impact of bpMRI, when compared to mpMRI, on detecting clinically significant prostate cancer using other accepted histological definitions of cancer significance in combination with staging criteria for clinical significance [[name] et al, 2011; Matoso and Epstein, 2019; [name] et al, 2012; Eggener et al, 2015; Ploussard et al, 2011].
- To evaluate the impact of the different MRI scores (on a scale from 1 to 5) on biopsy recommendations, and potential subsequent diagnosis of clinically significant and clinically insignificant prostate cancers, using all histological thresholds of significance, and within each randomised group.
- To investigate clinical risk factors (age, total PSA, PSA-density, family history, ethnicity, prior prostate biopsy before the 2 years exclusion criteria) in relation to diagnosis of clinically significant prostate cancer using all the definitions of significance.
- Detection rates for each randomised group following each randomisation of known risk groupings. These are D'Amico [D'Amico et al, 1998], National Comprehensive Cancer Network (NCCN) [Mohler et al, 2019] and Cambridge Prognostic Groups (CPG) [Gnapragasam et al, 2018].
- To compare the Likert and PIRADS [latest version as defined in MRI Reporting SOP] reporting schemes in terms of proportions biopsied, and subsequently diagnosed with clinically significant and clinically insignificant prostate cancers, within each randomised group, using all histological thresholds of significance.
- Patient reported outcome and experience measures using validated questionnaires.

 To evaluate the impact of difference centres by size, stratified by MRI scanner type, biopsy route and amount of systematic biopsies taken, on cancer detection rates and patient reported outcomes.

Health economics

- To estimate incremental cost to the NHS and Personal Social Services (PSS) and incremental cost per clinically significant cancer detected and incremental cost per correct diagnosis.
- Modelled healthcare resource utilisation, NHS and PSS costs and incremental cost per QALY of using bpMRI compared to mpMRI; and using image-fusion compared to visual-registration. The model will incorporate the costs and impacts of potential changes in rates of biopsy and cancer treatment with different types of MRI and different type of biopsy strategy

2.3 Primary Endpoint

Randomisation-1: bpMRI versus mpMRI

Proportion of clinically significant cancers, defined as any amount of Gleason >/=3+4 (ISUP Grade Group >/=2) on biopsy, detected in the randomised population of patients at risk.

Randomisation-2: Visual-registration targeting versus image-fusion targeting

Proportion of clinically significant cancers, defined as any amount of Gleason >/=3+4 (ISUP Grade Group >/=2) on biopsy, detected in the randomised population of patients biopsied for a suspicious MRI.

2.4 Secondary Endpoints

Clinical

In each of the randomised groups, secondary outcomes are:

- MRI and biopsy-related adverse events and serious adverse events
- The proportion of patients advised to undergo a needle biopsy and the proportion of
 patients undergoing a prostate biopsy after MRI. We will document common reasons for
 patients who are advised to undergo a biopsy who decline and reasons for patients who
 are advised against a needle biopsy who still choose to have a biopsy. We shall record
 the number of patients with a non-suspicious bpMRI/mpMRI that are recommended for
 biopsy and the types cancers subsequently detected.
- The proportion of patients diagnosed with clinically insignificant prostates cancers, defined as any Gleason 3+3=6 on needle biopsy carried out after MRI. These will also be stratified by MRI score, presence of clinical risk factors and whether the biopsy was carried out on clinician recommendation or patient choice.
- The proportion of patients diagnosed with clinically significant and clinically insignificant prostate cancers using other histological thresholds, on prostate biopsy carried out after MRI. Similarly, as above, we will also evaluate these proportions by MRI score at patient and lesion level (on a scale of 1 to 5) and by presence or absence of clinical risk parameters.

- The proportion of patients diagnosed with clinically significant and clinically insignificant prostate cancers using all histological thresholds on targeted biopsy using 4 targeted cores only compared to 6 targeted cores for the first targeted lesion.
- Detection rates for each randomised group of known prognostic risk categories. These are D'Amico, National Comprehensive Cancer Network (NCCN) and Cambridge Prognostic Groups (CPG).
- A comparison of the two MRI scoring systems, Likert and PIRADS [latest version as defined in MRI Reporting SOP], in terms of the proportion of patients biopsied and subsequently diagnosed with clinically significant and clinically insignificant prostate cancer, using each of the histological thresholds, on a prostate biopsy. Our study would be an opportunity to conduct a robust comparison of the two reporting systems in a large sample and allow inclusion in meta-analyses with studies that used either one alone.
- Characteristics of cancer in targeted versus systematic biopsies and by MRI score, PSA, PSA density, age, ethnicity, family history and history of prior prostate biopsy with a multivariable evaluation to determine patients might avoid systematic sampling in future.
- External validation of the Imperial RAPID Risk Score (MRI+) and Imperial RAPID Risk Score (Systematic+) within each randomised group of the IP7-PACIFIC study
- Impact of prostate biopsy in each randomised group on patient reported outcomes and patient reported experience measures using an updated version of the Prospective cohort study (Prostate Biopsy Effects: ProBE) questionnaire [Rosario et al, 2012] and the EQ-5D-5L health-related quality of life questionnaire, and stratified by type of biopsy (transrectal vs. transperineal; for transperineal biopsy, limited systematic vs. sectoral systematic.
- Analysis of biopsy rates and detection of cancer (by all histological thresholds) as well as patient reported outcomes and experience measures in randomised group will be conducted by centre using centre size. MRI scanner type (1.5Tesla vs. 3.0Tesla), type of biopsy route used (transrectal vs. transperineal), number of systematic biopsy taken (limited systematic vs. extended systematic biopsy), type of analgesia/anaesthetic (local anaesthetic, sedation or general anaesthetic) as additional stratification factors.

Definitions of clinical significance on biopsy

As well as the primary outcome definition of any amount of Gleason 3+4 or greater on any one or more biopsy cores, we will also use the following histological thresholds:

i) any amount of Gleason 4+3=7 or more

ii) any amount of Gleason >/=4+3 OR Gleason 3+3=6 of >/=6mm (PROMIS definition 1)

iii) any amount of Gleason >/=3+4 OR Gleason 3+3=6 of >/=4mm (PROMIS definition 2)

iv) any amount of Gleason >/=3+4 OR Gleason 3+3=6 of >/=6mm

v) Gleason 3+4=7 with >10% pattern 4 OR cribriform pattern OR a ductal component

Health economic

- Incremental cost per clinically significant cancer detected and incremental cost per correct diagnosis.
- Modelled healthcare resource utilisation, NHS and PSS costs and incremental cost per QALY of using bpMRI compared with mpMRI. The model will incorporate the costs and impacts of potential changes in rates of biopsy and cancer treatment with different types of MRI.
- Modelled healthcare resource utilisation, NHS and PSS costs and incremental cost per QALY of using image-fusion compared to visual-registration

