The histological report will evaluate the following aspects for each target and each location of systematic biopsies carried out according to Royal College of Pathology (UK) guidance [Royal College of Pathology Guidelines, 2016]: number of biopsies, number positive for cancer, core length in mm, cancer presence, maximum cancer core length in mm (where continuous and discontinuous numbers are given, for the purpose of analysis, the continuous number will be used), primary, secondary and highest Gleason grade, percent pattern 4 and presence of cribriform pattern when Gleason 3+4, perineural invasion/lymphovascular invasion/intraductal components/neuroendocrine differentiation; and vii) other features (high grade prostatic intraepithelial neoplasia/atypical acini/inflammation/atrophy). See Biopsy Reporting SOP.

Definition of clinically significant prostate cancer on histology

We know that some prostate cancers are clinically significant, and that other prostate cancers are clinically insignificant. Whilst there is still some uncertainty about exactly what entails clinical significance, particularly with respect to whether patients diagnosed with low volume Gleason 3+3 or Gleason 3+4 cancer should be on active surveillance, most physicians, researchers and guideline panels agree detection of Gleason >/=3+4 (ISUP grade Group >/=2) is the key target condition for any screening or diagnostic pathway. As a result, this is the primary histological threshold we will measure.

There is also acknowledgement that a low amount of cancer or low percent pattern 4 is perhaps not as aggressive. So, whilst the primary outcome measure will be the detection of any Gleason >/=3+4, there are important secondary definitions of clinical significance that we will measure as well. These definitions will incorporate the wide and divergent views on clinical significance but incorporate evidence on the amount of pattern 4 and maximum cancer core length as being significant elements [26-30]. These definitions will be:

- any amount of Gleason 4+3=7 or more
- any amount of Gleason >/=4+3 OR Gleason 3+3=6 of >/=6mm (PROMIS definition 1)
- any amount of Gleason >/=3+4 OR Gleason 3+3=6 of >/=4mm (PROMIS definition 2)
- any amount of Gleason >/=3+4 OR Gleason 3+3=6 of >/=6mm (PROMIS definition 3)

- any amount of Gleason 3+4=7 with cribriform pattern or a ductal component or >/=10% pattern 4 or any Gleason >/=4+3 [van Leenders et al, 2020].

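### Secondary definition (ii), labelled PROMIS definition 1, omits Gleason 3+4 at every length, so it is not ordered by grade and contradicts the protocol's own rationale

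*Protocol*

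**What the plan says.** Protocol section 2.4 (Definitions of clinical significance on biopsy) starts from the "primary outcome definition of any amount of Gleason 3+4 or greater on any one or more biopsy cores" and adds five secondary thresholds. Four of them matter here:

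- Threshold (i) is a pure grade rule: Gleason 4+3 or higher, in whatever quantity.
- Threshold (ii), the one at issue, reads "any amount of Gleason >/=4+3 OR Gleason 3+3=6 of >/=6mm (PROMIS definition 1".
- Threshold (iii), labelled PROMIS definition 2, lowers the grade limb to 3+4 and admits 3+3 from 4 mm.
- Threshold (iv) has the same grade limb as (iii) but admits 3+3 only from 6 mm.

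Section 5 (Definition of clinically significant prostate cancer on histology) repeats (ii) in the same terms. The Trial Summary names PROMIS 1 and 2 without spelling them out. Nothing in the protocol corrects the wording.

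Section 5 also says why the secondary definitions exist: they "incorporate evidence on the amount of pattern 4 and maximum cancer core length as being significant elements". They feed a stated secondary endpoint in each randomised group: "The proportion of patients diagnosed with clinically significant and clinically insignificant prostate cancers using other histological thresholds".

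**The concern.** In (ii) the grade limb starts at Gleason 4+3 and the length limb is tied to Gleason 3+3. Gleason 3+4 falls between them. Read literally, 6 mm of 3+3 is significant, 10 mm of 3+4 is not, and any amount of 4+3 is. Lengthening a cancer or adding pattern 4 should never make it less significant under the section 5 rationale, yet here adding pattern 4 can.

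At stake is the meaning of one secondary endpoint wherever it is reported: bpMRI against mpMRI, image-fusion against visual-registration, by MRI score, Likert against PIRADS, and 4 against 6 targeted cores. A count under (ii) would mix long 3+3 with 4+3 and higher and leave out the grade between them, so a difference in (ii) would be hard to interpret.

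This is not a detail left to the statistical analysis plan. The protocol fixes the rule in words twice. A plan that follows it inherits the gap, and a plan that departs from it contradicts the protocol.

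**Working it through.** No figure of the plan needs reproducing, because the question is one of logic.

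**Step 1: classify each combination.** The inputs are the primary definition and (i) to (iv) from section 2.4, applied to a single cancer. The last row is the repair proposed below.

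| Definition | 3+3, under 4 mm | 3+3, 4 to under 6 mm | 3+3, 6 mm or more | 3+4, under 6 mm | 3+4, 6 mm or more | 4+3 or higher |
|---|---|---|---|---|---|---|
| Primary | no | no | no | yes | yes | yes |
| (i) | no | no | no | no | no | yes |
| (ii) as written | no | no | **yes** | no | **no** | yes |
| (iii) | no | yes | yes | yes | yes | yes |
| (iv) | no | no | yes | yes | yes | yes |
| (ii) repaired | no | no | yes | no | yes | yes |

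**Step 2: look for reversals.** A reversal is a pair of equal length in which the higher grade is not significant and the lower grade is. Over whole lengths of 1 to 15 mm, (ii) as written reverses between 3+3 and 3+4 at every length from 6 to 15 mm (10 of 10). The primary definition, (i), (iii) and (iv) have none. Definition (i) excludes 3+4 but also excludes all 3+3. Definitions (iii) and (iv) start their grade limb at 3+4.

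**Step 3: per core or per patient.** Take a man with one core of 6 mm Gleason 3+3 and another of 2 mm Gleason 3+4.

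- Rule applied core by core: the first core qualifies, so he is significant.
- Rule applied to the highest grade per patient: grade 3+4, longest core 6 mm, so he is not significant.

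In the comparison of 4 with 6 targeted cores, the second reading lets two further cores move a man out of the significant group. Under the first reading, the reversal occurs only when the qualifying cancer itself is graded 3+4.

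**Step 4: compare the two obvious repairs.**

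- Start the grade limb at 3+4: (ii) becomes identical to (iv) and adds nothing.
- Attach the 6 mm limb to cancer of any grade: no reversals remain. It differs from (i) by adding 3+3 and 3+4 of 6 mm or more. It differs from (iv) by excluding 3+4 under 6 mm.

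**Step 5: illustrate the size.** The 38% detection rate comes from section 8.1. The protocol gives neither the share of these cancers that are 3+4 nor the share of those reaching 6 mm, so both are assumptions: 50-75% and 30-60%.

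- Low: 38 × 0.50 × 0.30 = 5.7 per 100 men
- High: 38 × 0.75 × 0.60 = 17.1 per 100 men

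On the 3230 men required before attrition in section 8.1, that is 32.3 × 5.7 = 184 to 32.3 × 17.1 = 552, both arms together.

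**The case against.** **Definition (ii) is one of five secondary thresholds.** A man with 10 mm of 3+4 is counted under the primary definition, (iii) and (iv), and grade and core length are recorded for each target and systematic location. This stands. No data are lost, and the point concerns a secondary endpoint only.

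**The 3+3 in the length limb may be shorthand for 3+3 or higher.** That is plausible given the section 5 rationale, but the text does not say so. A programmer coding from the protocol would produce the gap. If this is what was meant, it supports the repair.

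**The reversal depends on the reading.** Partly true. The primary definition is judged on any one or more cores. If (ii) is judged the same way, a separate 3+4 core does not cancel a qualifying 3+3 core. The omission of 3+4 itself holds under either reading.

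**A reader might infer that (ii) is the only definition out of order.** That is not so. Definition (v) in section 2.4, taken literally, covers 3+4 with certain features but not 4+3 or higher without them. Section 5 adds 4+3 or higher as a separate limb. The uniqueness claim holds only among the length-based definitions (ii) to (iv).

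**A reader might also infer that the better test is penalised.** The documents do not show this. Regrading long 3+3 as 3+4 lowers (ii), but better targeting may raise it by finding more 4+3 or longer 3+3. The net direction is unknown.

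**Conclusion.** The definition is wrong as written. It leaves out Gleason 3+4 at any length while counting 3+3 of 6 mm or more, in conflict with the reason section 5 gives for having these definitions. This rests on the text alone and needs no outside source. It distorts one secondary endpoint wherever that endpoint is compared, and leaves the primary endpoint and the sample size untouched.

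The 6 to 17 per 100 men is an illustration on assumed shares. It sizes the group omitted from (ii) in both arms together. It is neither a count of men who would be reclassified between tests nor a between-arm bias.

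A reader might conclude that the protocol misquotes the study named in the label. That cannot be decided from the document, and the verdict does not depend on it.

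**What to change.** In sections 2.4 and 5, reword (ii) as: any Gleason 4+3 or higher, or a maximum cancer core length of at least 6 mm for cancer of any Gleason grade. This removes every reversal and keeps (ii) distinct from (i) and (iv). The sponsor should confirm the wording against the source named in the label. If the literal rule is really intended, drop the PROMIS label and say why 3+4 is left out. State also whether (ii) is applied core by core or per patient.

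In the same edit, reconcile (v) in section 2.4 with its counterpart in section 5, which includes 4+3 or higher.

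The cost is a wording change to two definitions in two sections. The histology report already captures grade and maximum cancer core length, so no new data collection, change in conduct or sample-size revision is needed.
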